6.5.6 Bone Mass

Dual-energy X-ray absorptiometry (BMD, TBS) data will be summarized using mean, standard deviation, minimum, maximum and median by treatment group and visit. The within-subject change will be calculated per visit as the post-baseline measurement minus the baseline measurement. The records marked as poor image quality will be excluded from the analysis. Change from baseline in bone mass density (BMD) and trabecular bone score (TBS) at hip and spine at 12 months will be derived for separate locations. An ANCOVA model, with treatment and smoking status (current vs former/never) as factors, with baseline weight and baseline value as covariates, will be used for treatment comparisons.

A sensitivity analysis will be performed by including patients with baseline but missing any post-baseline value, assuming no changes (the change score to be 0).

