5.8.7 Adverse Events of Special Interest

AEs of special interest are AEs the sponsor may wish to carefully monitor. These AEs may be serious or non-serious and are not considered SAEs unless they meet the SAE definition in [Section 5.8.1 Definition of Adverse Events](#). AEs of special interest should be reported on the eCRF as such.

If the AE of special interest meets the definition of an SAE, they are to be collected via the SAE/Special Situation worksheet and reported within 24 hours as described in [Section 5.8.5 Reporting of Serious Adverse Events \(SAEs\)](#). Adverse events of special interest in this study will include:

- AE of uterine bleeding
- Endometrial hyperplasia/cancer or disordered proliferative endometrium
- AE of thrombocytopenia
- AE of liver test evaluations
- AE of bone fractures/bone loss $\geq 7\%$
- AEs of abuse liability
- AEs of depression
- AEs of wakefulness
- AEs of effect on memory

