7.6 Analysis of Safety

Overall long-term safety of fezolinetant will be the primary objective of this study. The safety assessments include adverse events, laboratory assessments, vital signs, C-SSRS, Pap test, physical examination, ECG, endometrial health assessment and imaging (mammogram, DXA, TVU). Safety analysis will be conducted on the SAF.

Primary Safety Variables:

The primary variable will require the evaluation of the safety of fezolinetant on the following:

- Frequency and severity of AEs
- Percentage of subjects with endometrial hyperplasia
- Percentage of subjects with endometrial cancer

Secondary Safety Variables:

- Change from baseline in endometrial thickness at 12 months
- Percentage of subjects with disordered proliferative endometrium
- Change from baseline in BMD and TBS at hip and spine at 12 months
- Vital signs: sitting systolic and diastolic blood pressure and pulse rate
- Laboratory tests: hematology, biochemistry and urinalysis
- C-SSRS
- ECG parameters

For each AE of special interests a summary statistics will be provided and the rate, odds ratio, and their corresponding 2-sided 95% confidence intervals will be presented. For the treatment comparison of bone density and endometrial thickness, an analysis of covariance model will be used. The model will include treatment and smoking status (current vs former/never) as factors, with baseline weight and baseline as covariates.

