6.5 Analysis of Safety

Overall long-term safety of fezolinetant and the effect of fezolinetant on endometrial health will be the primary objective of this study. The safety assessments include adverse events, laboratory assessments, vital signs, C-SSRS, ECG, endometrial health assessment and imaging (mammogram, DXA, TVU). In all analysis of safety, the treatment group includes placebo, fezolinetant 30mg, fezolinetant 45mg and fezolinetant total will be presented by treatment group for SAF, unless specified otherwise. For analyses by visit, the analysis windows from Section 6.10.1 will be applied. Except for adverse events and follow-up visit data, only data up to one day after the last dose date will be considered for the analyses.

The baseline value for safety endpoint will be the last non-missing value taken on or prior to first dose of study drug unless otherwise noted.

Primary Safety Variables

- Frequency and severity of AEs.
- Percentage of subjects with endometrial hyperplasia.
- Percentage of subjects with endometrial cancer.

Secondary Safety Variables

- Change from baseline in endometrial thickness at 12 months.
- Percentage of subjects with disordered proliferative endometrium.
- Change from baseline in bone mass density (BMD) and trabecular bone score (TBS) at hip and spine at 12 months.
- Change from baseline to each timepoint in vital signs: sitting systolic and diastolic blood pressure and pulse rate.

- Change from baseline to each timepoint in laboratory tests: hematology, biochemistry and urinalysis.
- C-SSRS at each timepoint.
- Change from baseline to each timepoint in ECG parameters

Exploratory Safety Variables

- Change from baseline to specified time points in serum concentrations of sex hormones and sex hormone-binding globulin (SHBG) (week 4, 12, 24, 52 and 55).
- Plasma concentration of fezolinetant and the fezolinetant metabolite ESN259564 at specified timepoints (week 4, 12, 24 and 52).

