- TEAEs excluding serious adverse events that equal to or exceed a threshold of 5.0% in any treatment group.

The number and percentage of subjects with TEAEs, as classified by PT only, will be summarized for each treatment group.

The number of TEAEs and the number and percentage of subjects with TEAEs, as classified by SOC and PT will be summarized by severity and by relationship to study drug. In the subject count, if a subject has multiple TEAEs with the same SOC or PT, but with differing severity or relationship, then the subject will be counted once with the worst severity and highest degree of relationship. If severity or relationship is missing for all episodes of the event, the subject will be counted under missing severity or relationship. In the adverse event count, the adverse events will be presented in each category they were classified to. Drug related TEAEs will be presented in a similar way by severity only.

Among TEAEs, following adverse events of special interest (AESI) are defined:

- Adverse event of endometrial hyperplasia/cancer or disordered proliferative endometrium
- Adverse event of liver test elevations
- Adverse event of uterine bleeding
- Adverse event of thrombocytopenia
- Adverse event of bone fractures
- Adverse event of abuse liability
- Adverse event of depression
- Adverse event of wakefulness
- Adverse event of effect on memory

Search terms defining the AESIs will be pre-specified and documented. The number and percentage of subjects with AESIs as classified by PT will be separately summarized for each treatment group.

The number and percentage of subjects with TEAEs associated with COVID-19, as classified by PT, will be summarized for each treatment group, fezolinetant total and overall.

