6.10 Additional Conventions

6.10.1 Analysis Windows

Study Day for analysis windows will be calculated as date of visit/assessment – first dose date +1.

Study Day for the follow-up (FUD) phase will be calculated as date of visit/assessment – last dose date of study treatment (Date of EOT).

Except for adverse events, for the analysis window (weeks prior to the follow-up period), the last day is always 1 day after the last day of exposure to double-blind treatment.

The end of overall treatment is defined as the last day of treatment +1 and the follow-up period begins at last overall treatment + 2 days and onward (Follow-up Study Day 2).

The data summary by visits will be done following the analysis windows specified in the table below:

Analysis	Scheduled	Analysis Windows (day)				
Visits	Day in Protocol	a)	b)	c)	d)	e)
Baseline	Day 1	Last non-missin	ng value on or prio	or to day 1 (inclu	sive)	
Week 2	Day 15	2 to 22				
Week 4	Day 29	23 to 43	2 to 43	2 to 57		
Week 8	Day 57	44 to 71	44 to 71			
Week 12	Day 85	72 to 99	72 to 99	58 to 127	2 to 127	
Week 16	Day 113	100 to 127	100 to 127			
Week 20	Day 141	128 to 155	128 to 155			
Week 24	Day 169	156 to 183	156 to 183	128 to 267	128 to 267	
Week 28	Day 197	184 to 211	184 to 211			
Week 32	Day 225	212 to 239	212 to 239			
Week 36	Day 253	240 to 267	240 to 267			
Week 40	Day 281	268 to 295	268 to 295			
Week 44	Day 309	296 to 323	296 to 323			
Week 48	Day 337	324 to 351	324 to 351			
Week 52	Day 365	352 to 376	352 to 376	268 to 376	268 to 376	2 to 376
Follow-up	Day 386	Last treatment + 2 days and onwards				

a) Apply to Clinical laboratory and urinalysis

b) Apply to Vital signs

- c) Apply to Blood PD/PK sample, EQ-5D-5L, MENQoL
- d) Apply to C-SSRS
- e) Apply to 12-lead ECG

For TVU and DXA, the week 52 analysis window is day 2 to last treatment + 30 days. For endometrial biopsy, refer to Section 6.5.5 for analysis window.

As a general rule, if more than one observation exists within the analysis window, the observation closest to the scheduled visit day will be selected for that visit. If there are two observations that have the same distance from the scheduled day, the value that is after the scheduled day will be selected in the analysis. If more than one observation is made on the same day, an average value if continuous or the worst value if categorical will be included in the analysis.

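### The one planned bone sensitivity analysis (missing change set to 0) cannot show whether unscanned fezolinetant women lost more bone, and the SAP omits the protocol's AESI of bone loss of 7% or more

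*SAP*

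**What the plan says.** The effect on bone mineral density is the trial's only secondary objective (Protocol 2.1.2, SAP 2.1). Change in BMD and TBS at hip and spine at 12 months is a secondary safety endpoint (SAP 5.2).

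For analysis, SAP 6.5.6 states:

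- Scale: "The within-subject change will be calculated per visit as the post-baseline measurement minus the baseline measurement". This is an absolute change.
- Model: ANCOVA with treatment, smoking status, baseline weight and baseline value.
- Unusable scans: "The records marked as poor image quality will be excluded from the analysis".
- Missing data: one sensitivity analysis, which adds women with a baseline and no post-baseline value, "assuming no changes (the change score to be 0"). No other missing-data analysis is planned for bone.

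For adverse events of special interest, Protocol 5.8.7 lists "AE of bone fractures/bone loss $\geq 7" (the threshold is 7% or more). Protocol 7.6 adds: "For each AE of special interests a summary statistics will be provided and the rate, odds ratio", with two-sided 95% intervals. The matching SAP 6.5.1 item is "Adverse event of bone fractures", with no mention of bone loss. The SAP's only percent change from baseline is for sex hormones and SHBG (SAP 6.5).

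On timing, SAP 6.5 says that, except for adverse events and follow-up visit data, "only data up to one day after the last dose date will be considered for the analyses". SAP 6.10.1 says: "For TVU and DXA, the week 52 analysis window is day 2 to last treatment + 30 days".

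**The concern.** A sensitivity analysis for a safety endpoint should put pressure on the no-harm reading: how much worse would the women without a scan have to be before the conclusion changed? Setting their change to 0 does not ask this. Both arms receive the same benign value, whatever happened to the women concerned. If the result agrees with the main analysis, readers may take it as evidence that missing scans hide nothing, and the interval around that result will look tighter than the scans support.

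The SAP also leaves open whether a woman whose only post-baseline scan is excluded for poor quality is then zero-filled.

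The AESI mismatch is a separate gap on the same endpoint. A mean difference can be small while a few women lose a lot. The protocol names such losses as of special interest, but nothing in the SAP text would summarise them.

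**Working it through.** **Inputs.** From the documents: 580 women per arm (SAP 3) and two-sided 5% tests (SAP 6.1). Neither document gives a DXA missing rate, an SD or an expected change for bone, so there is no bone figure to reproduce. Assumed: SD of change = 1, so results are in SD units and hold for absolute change; all 580 have a usable baseline; missing shares p (placebo) and q (drug) of 10-40%; mean placebo change b from 0 to -1 SD (-0.33 where one value is shown). The observed difference d is drug minus placebo, so negative is harm. Covariate adjustment is ignored.

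**Formulas.**
- Zero-fill difference = (1-q)d + (p-q)b. With p = q = m this is (1-m)d.
- Main 95% half-width = 1.96 × √[1/(580(1-p)) + 1/(580(1-q))].
- Zero-fill variance in an arm with missing share m and mean μ = (1-m)(1+μ²) - ((1-m)μ)²; half-width = 1.96 × √(sum of the two variances / 580).

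**Equal missing shares.** Example at 20%, d = 0, b = -0.33: main 1.96 × √(2/464) = 0.129. Zero-fill variance is 0.8 × 1.1089 - 0.264² = 0.8174, so the half-width is 1.96 × √(2 × 0.8174/580) = 0.104.

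| Missing, each arm | Difference × | Main half-width | Zero-fill half-width (d = 0, b = -0.33) | Main z at d = -0.15 | Zero-fill z at d = -0.15, b from 0 to -1 |
|---|---|---|---|---|---|
| 10% | 0.90 | 0.121 | 0.110 | -2.42 | -2.42 to -2.29 |
| 20% | 0.80 | 0.129 | 0.104 | -2.28 | -2.28 to -2.06 |
| 30% | 0.70 | 0.138 | 0.098 | -2.14 | -2.13 to -1.84 |
| 40% | 0.60 | 0.149 | 0.091 | -1.98 | -1.97 to -1.64 |

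At 10-20% the test statistic barely moves. At 30-40% it can cross 1.96. Take 40%, b = -0.33, d = -0.15: the variances are 0.6261 (placebo) and 0.6553 (drug), so the half-width is 1.96 × √(1.2814/580) = 0.092. Zero-fill gives -0.090 ± 0.092 (-0.182 to +0.002); the main analysis gives -0.150 ± 0.149 (-0.299 to -0.001). At 30% the crossing needs heavier background loss: z = -1.84 at b = -1.

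**Unequal missing shares, b = -0.33.**
- 10% placebo, 20% drug, d = 0: (0.10 - 0.20)(-0.33) = +0.033 in the drug's favour.
- Same shares, d = -0.15: 0.8(-0.15) + 0.033 = -0.087 ± 0.108, which includes 0. The main analysis gives -0.150 ± 0.125, which does not.
- 20% placebo, 10% drug, d = -0.15: 0.9(-0.15) + 0.10(-0.33) = -0.168, which overstates harm.

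With d ≤ 0 and b < 0, zero-fill overstates harm only if (p-q)|b| > q|d|, which requires more missing scans on placebo.

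**What it does not test.** Suppose scanned women show d = 0, but unscanned drug women lost a further δ. The all-women difference is then -mδ, and it leaves the reported interval once δ exceeds half-width/m. At 10/20/30/40% missing that is 1.21/0.64/0.46/0.37 SD for the main interval and 1.10/0.52/0.33/0.23 SD for the zero-fill interval. The main analysis has the same blind spot; zero-fill narrows the interval without examining it.

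**The 7% item.** Absolute change cannot stand in for it. For assumed baseline BMD of 0.70 to 1.20 g/cm², 7% is 0.049 to 0.084 g/cm², and a fixed loss of 0.06 g/cm² is 8.6% at one end and 5.0% at the other. The SAP's change list (7.1) attributes its AESI edits to agreement with protocol version 2.1. The current Protocol 5.8.7 still carries the bone-loss item.

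**The case against.** **Few women may be imputed.** Protocol 5.5.2 asks for a DXA soon after drug discontinuation in women who withdraw. The EOT/ED visit must be in clinic even under the COVID-19 provisions, and the SAP 6.10.1 window lets early-discontinuation scans count as week 52. Zero-fill therefore reaches only women with no usable post-baseline scan. The 60% allowance in the sample-size section concerns biopsies, and the 81% completion in the phase 2b study is not a DXA rate; neither supports a high missing share here. This stands and limits the size: at 10% missing only an extreme shift matters, and the 30-40% rows are hypothetical.

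**It is a choice of method without a formal test.** Also true. No bone margin, power claim or decision rule depends on it. But an analysis offered as a robustness check should be able to reveal the problem it checks for.

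**The AESI is an adverse event, not a DXA variable.** Protocol 5.8.7 has AESIs reported on the eCRF, and SAP 6.5.1 leaves search terms to separate documentation, which could capture reported bone-loss events. This also stands. A DXA-derived count has a different source and denominator, so it supplements the AESI rate and does not replace it. The protocol itself gives no site or calculation for the threshold.

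**The two time limits.** A reader might infer that the one-day limit in SAP 6.5 removes late DXA scans. SAP 6.10.1 names DXA and TVU specifically and reads as an exception, and neither is scheduled at week 55. Because data beyond one day after last dose are also assigned to Follow-up, one line on precedence would help; it is no more than that.

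**Conclusion.** The point holds in two parts.

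First, the only bone sensitivity analysis does not examine worse loss among unscanned fezolinetant women. With equal missing shares it shrinks the difference by (1-m) and tightens the interval. At 10-20% missing it largely restates the main result on a smaller scale; at 30-40% with background bone loss it can also turn a detected harm into an interval that includes 0. These sizes rest on assumed missing shares, SD and background change.

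Two stronger readings are tempting and not supported. One is that zero-fill always favours the drug: when observed harm is zero or negative and both arms lose bone, it does so with more missing on drug, but with more missing on placebo it can overstate harm. The other is that it is harmless because a real difference would still be detected: that fails at the higher missing shares.

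Second, the protocol and SAP AESI lists disagree on bone loss, and the SAP text defines no percent change from which a 7% loss could be counted. A reader might infer that no such summary will exist. The documents do not establish that, because search terms and table specifications are held elsewhere.

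Both parts affect estimation and interpretation of the secondary objective, not a formal test. They are worth fixing before database lock.

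**What to change.** Before database lock:

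(a) In SAP 6.5.6, keep zero-fill as supportive. Add multiple imputation by arm using baseline value, weight and smoking status, followed by a delta (tipping-point) analysis that worsens the imputed values of unscanned fezolinetant women over a stated range, for example 0 to 1.0 SD of change in steps of 0.25, for each dose against placebo. State that a woman whose only post-baseline scan is of poor quality counts as missing. Report missing DXA by arm.

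(b) Reconcile Protocol 5.8.7 and SAP 6.5.1 so that reported bone-loss events are summarised on the SAF with the rate and odds ratio that the protocol plans. In addition, define percent change as 100 × (post-baseline - baseline)/baseline by site, and tabulate women with a loss of 7% or more by arm, with rate and odds ratio, among those with usable paired scans. Label this as a DXA-derived supplement to the adverse-event AESI.

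(c) Add one line to SAP 6.5 saying that the 30-day DXA/TVU window takes precedence over the one-day limit.

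The cost is SAP wording and programming on scans already planned, with no new data. The downsides are extra output and a delta range that is a matter of judgment and must be justified in advance.

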6.5.7 Other Safety-Related Assessments

C-SSRS

C-SSRS (including suicidal ideation and suicidal hehavior) results at each visit including baseline will be summarized by treatment group.

Imaging

A mammogram at week 52/EOT/ED will be conducted if it coincides with the regularly scheduled routine screening mammogram of the patient, in accordance with local medical practice guidelines and the patient's primary care physician. Mammogram results will only be listed, if applicable.

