The sample size is not calculated based on the statistical power for efficacy evaluation to detect treatment difference, as the primary objective of this study is to assess long-term safety.

The total sample size will be 1740 subjects who will be randomly assigned 1:1:1 to fezolinetant 45 mg once daily group (580); fezolinetant 30 mg once daily group (580) and placebo group (580). This sample size would provide high probability to observe events of special interest that has with a fairly low background event rate that is less than 1%. If an assumed background rate of 0.26% such as for endometrial hyperplasia, this sample size would be able to demonstrate that the point estimate is less than or equal to 1% and upper bound of one-sided 95% CI to be $\leq 4\%$ with at least 95% probability, assuming up to 60% (including baseline, ED and subject refusal of endometrial biopsy at EOT) of subjects may not have evaluable biopsy data.

Safety:

Safety analyses will be performed on the safety analysis set (SAF), which is defined as all subjects who received at least 1 dose of study medication.

Endometrial health-related endpoints such as hyperplasia, cancer and proliferative endometrium will be analyzed on the endometrial health analysis set (EH set). The EH set is defined as subjects having 1 year evaluable biopsy results.

The number and percentage of treatment-emergent adverse events (TEAEs) reported during the study period will be summarized by system organ class, preferred term, seriousness, severity and relationship to treatment, overall and by treatment group. The rate of endometrial hyperplasia, cancer and disordered proliferative endometrium will be evaluated separately.

Changes from baseline for vital signs, ECGs and laboratory assessments will be summarized in tables by treatment group and visit.

Descriptive summary statistics and listing of events will be provided for the C-SSRS by timepoint and for the entire study.

Efficacy:

No efficacy data will be collected.

Exploratory Endpoints:

The exploratory endpoints include the MENQOL and EQ-5D-5L which will be assessed at baseline and weeks 4, 12, 24 and 52. The exploratory endpoints will be analyzed for the full analysis set (FAS). Summary statistics will be provided by treatment group.

Pharmacokinetics:

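### The SAP omits the whole-study C-SSRS summary and listing promised in the protocol synopsis, and its one-record-per-window rule can keep a positive early-discontinuation response out of every planned C-SSRS table

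*SAP*

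**What the plan says.** C-SSRS is a secondary safety endpoint (SAP 5.2). The Statistical Methods part of the protocol synopsis states: "Descriptive summary statistics and listing of events will be provided for the C-SSRS by timepoint and for the entire study". Protocol 7.6 lists C-SSRS as a secondary safety variable and adds nothing on how it is summarised.

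In the SAP, section 6.5 names the variable as "C-SSRS at each timepoint", and section 6.5.7 says that "results at each visit including baseline will be summarized by treatment group". No whole-study summary and no C-SSRS listing appears in the SAP. The list of changes in SAP 7.1 does not record a decision to remove either.

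SAP 6.10.1 assigns C-SSRS to window column d: Days 2-127 for Week 12, 128-267 for Week 24 and 268-376 for Week 52. Its default selection is that "if more than one observation exists within the analysis window, the observation closest to the scheduled visit day will be selected for that visit". Ties go to the later record. The worst value is taken for a categorical variable only when several records share a day. Records from two days after last dose onward belong to follow-up, where again one record is kept, the one nearest Day 386. SAP 6.5 sets the matching cut-off: apart from AEs and follow-up visit data, "only data up to one day after the last dose date will be considered for the analyses".

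The protocol schedule (Table 1, footnote t) requires C-SSRS at screening, Day 1, Weeks 12 and 24, EOT/ED and Week 55.

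**The concern.** For a rare safety outcome the useful figure is the number of distinct subjects with any post-baseline suicidal ideation or behaviour. By-visit tables do not give it: one subject may be positive at several visits, so the visit counts cannot be added.

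The selection rule adds a second problem. A subject who stops early has a protocol-required ED assessment that may share a window with a routine visit already made. If the routine record is nearer the scheduled day, the ED response goes into no C-SSRS table, whatever it shows. For a count of subjects ever positive, this can only lower the figure.

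The SAP protects against this elsewhere. Liver categories use the subject's highest value (6.5.2.1), and the more severe biopsy result is counted when there are several (6.5.5). C-SSRS has no counterpart.

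**Working it through.** **The plan's own figure.** The documents give no figure for C-SSRS. Their only rare-event figures are the detection probabilities for 580 subjects per arm (Protocol 7.1, SAP 3). These reproduce: at a 0.20% rate, 1 - 0.998^580 = 68.69%. They take every event as counted and say nothing about record selection.

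**Inputs.** Windows, nearest-day rule, tie rule and follow-up rule from SAP 6.10.1; the one-day cut-off from SAP 6.5; C-SSRS visits from Protocol Table 1 (Week 12 = Day 85, Week 24 = Day 169, Week 52 = Day 365).

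**Window lengths.** 127 - 2 + 1 = 126 days; 267 - 128 + 1 = 140 days; 376 - 268 + 1 = 109 days.

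**Case 1: ED assessment one day after last dose.** The ED response is positive; earlier scheduled visits are on their nominal days and negative. Possible ED days are 2 to 364, so 363 days.

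| ED day | Records in the window | Record kept | Positive shown? | Days |
|---|---|---|---|---|
| 2-85 | ED only | ED | yes | 84 |
| 86-127 | Day 85 and ED | Day 85 (distance 0) | no | 42 |
| 128-169 | ED only | ED | yes | 42 |
| 170-267 | Day 169 and ED | Day 169 (distance 0) | no | 98 |
| 268-364 | ED only | ED | yes | 97 |

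Discarded: 42 + 98 = 140 of 363. Kept: 84 + 42 + 97 = 223 of 363.

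Sensitivity to visit timing: if both routine visits fall 3 days early (Days 82 and 166) or 3 days late (Days 88 and 172), their distance is 3. ED positives are then lost from Day 89 and from Day 173: (127 - 89 + 1) + (267 - 173 + 1) = 39 + 95 = 134 days. The result barely moves.

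**Case 2: ED assessment two or more days after last dose.** The record moves to follow-up and competes with the visit about 21 days after last dose. The SAP's Day 386 can be read in two ways.
- As days from last dose: an ED record at +2 is 384 days from 386 and one at +14 is 372; the follow-up record at +21 is 365. The follow-up record is kept.
- As study day, for example last dose on Day 120, ED on Day 125 and follow-up on Day 141: distances 261 and 245. The follow-up record is kept.

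A negative follow-up record displaces the ED positive in each of these examples.

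**Case 3: completer with scheduled assessments only.** There is one record per window, so nothing is lost.

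**Case 4: completer with an additional unscheduled assessment, if one is made.** With negatives on Days 85, 169 and 365, a positive on any other day from 2 to 364 (363 - 2 = 361 days) is discarded.

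**With a worst-value summary over all post-baseline records,** the Case 1 loss is 0 of 363 days, and nothing is lost in Cases 2 and 4.

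**The case against.** The best defence is that the SAP is silent and has not withdrawn anything. It presents itself as elaborating the protocol and sends table and listing formats to TLF specifications that are not among these documents. The synopsis commitment may be met there. This stands as far as it goes: a reader might infer a deliberate removal, and the documents do not show one. But the SAP is where the analysis is fixed, and it commits only to by-visit results.

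A reader might also infer that a positive could vanish from every table in the report. That goes too far. Protocol 5.8.1.1 requires a clinically significant abnormal safety assessment to be reported as an AE, TEAE tables are not subject to window selection, and depression is an AESI. The route depends on the investigator's judgement, so it is a partial safeguard and does not replace a systematic C-SSRS count.

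Three further limits hold. A reader might infer that the rule tends to drop ED positives; in Case 1 it keeps them on 223 of 363 days. The protocol allows unscheduled visits but does not provide for C-SSRS at them, so Case 4 is conditional. And the rule is the same in all blinded arms: it can lower counts, but nothing in the documents shows a different loss between arms.

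The wide windows are not themselves a fault. They follow from a sparse schedule and bring off-schedule ED records into a visit summary.

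**Conclusion.** The point holds in limited form. The SAP does not carry over the synopsis commitment to a whole-study C-SSRS summary and listing. Followed as written, its selection rule can leave a positive, protocol-required ED response out of every planned C-SSRS table.

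The loss needs a second record in the same window or in follow-up, with the positive one not selected. For ED one day after last dose this covers 140 of 363 possible days (134 if routine visits are 3 days off schedule), assuming the routine visits are negative. These are counts of days. The documents give neither the distribution of ED timing nor a C-SSRS positive rate, so no number of lost subjects or change in percentage can be derived. The primary endpoints are not affected.

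The gap should be closed because this is a long-term safety trial in which each such event matters and the remedy is small.

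**What to change.** In SAP 6.5.7 add the synopsis's whole-study summary: the number and percentage of subjects in each treatment group with any post-baseline suicidal ideation, by worst category, and with any post-baseline suicidal behaviour. State that it uses all post-baseline records (scheduled, ED, follow-up and any unscheduled) and that neither the nearest-day selection nor the one-day cut-off applies to it. Add the promised listing of C-SSRS events.

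The by-visit table and the windows in SAP 6.10.1 can stay as they are; a worst-value rule within windows is unnecessary once the any-time table exists.

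Cost: one table, one listing and a few lines of SAP text. No new data are needed.
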